4.1. Background

Opioid analgesia is the primary pharmacologic intervention for managing pain in hospitalized patients¹. Opioid therapy is indeed the gold standard for treatment of post-surgical pain in hospital ward but also the majority of non-surgical patients admitted in hospital are exposed to opioids². They can be administered orally, by Patient Controlled Analgesia (PCA), by epidural or intrathecal infusions, by intravenous or intramuscular analgesia. In recent years there have been increasing concerns over unmonitored mortality and morbidity in patients during opioid therapy for acute pain³. Up to 80% of patients who received opioid analgesics experience Opioid-Related Adverse Drug Events (ORADEs)⁴. In post-surgical patients, ORADEs have been shown to significantly increase patient's hospital length of stay and related costs⁴. Improper patient monitoring has been reported by the Joint Commission as one of the main causes of ORADEs^{1,5}.

One of the major opioid side effects includes respiratory depression (RD), which causes alveolar hypoventilation and hypoxemia. The reported incidence of RD in post-surgical patients varied from 0.3% to 3.4% when only considering intervention rate (i.e. naxolone infusion)^{3,6,7}, while it is reported up to 21% and 41% when including also prolonged oxygen desaturation and bradypnea episodes, respectively^{6,8}. If detected early, most cases of opioid-related RD can be treated with naloxone; however, severe cases can be fatal⁹.

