Main risk factors for developing RD have been widely studied in literature, particularly for post-surgical patients. Most reported include: sleep apnea, obesity, snoring, old age, post-surgery, increased opioid dose requirement, concomitant use of other sedating medications, comorbidities like preexisting pulmonary or cardiac disease, PCA use and smoking^{1,4,7,16,17}.

The need of a simple tool to stratify patients at risk to develop RD has been underlined by several authors^{1,7,16,17}. Such a tool will also help health care providers in selecting the best candidate for capnographic monitoring. Previous attempts to develop prediction scores failed to show a significant sensitivity, probably due to limited sample size and retrospective design¹⁷ or were only limited to surgical patients⁷.

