8.4. Exclusion Criteria

- 1. Expected length of stay ≤ 24 hours.
- 2. Patient is receiving intrathecal opioids.
- 3. Post-surgical patients with American Society of Anesthesiologists physical status (ASA PS) V or higher.
- 4. Patients with the status of Do Not Resuscitate (DNR), hospice, or receiving end of life therapy.
- 5. Ventilated or intubated patients.
- 6. Patient is unwilling or unable to comply fully with study procedures (including non-toleration of the capnography cannula) due to any disease condition which can raise doubt about compliance and influencing the study outcome.
- Patient is a member of a vulnerable population, includinglegal incapacity or evidence that a subject cannot understand the purpose and risks of the study, regardless of authorized representative support.
- 8. Patient is participating in another potentially confounding drug or device clinical study.

9. Study Procedures

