13.1.1. Derivation Cohort Sample Size

The size of the derivation cohort has been calculated to provide at least 10 events per variable that we expect to enter into the logistic regression model. Recording at least 120 RD events would allow around 12 predictor variables to be entered into logistic regression. Assuming an incidence of 12% of subjects with RD episodes and 12-variables for prediction rule, a sample size of 1000 subjects is needed for the derivation cohort.

The selection of 12 high risk variables for the prediction rule has been based on literature review^{1,4,7,16,17,22}:

- Age > 65 y.
- Known or suspected sleep-disordered breathing (OSA, snoring, etc.).
- High risk surgery \leq 24 hours.
- PCA or epidural or intrathecal therapy.
- Obese (BMI >30).
- Multiple opioid or concurrent CNS/sedating medication (benzodiazepines, sleep aids, muscle relaxant, etc.).
- High opioid dosage (>30mg oral morphine per day or equivalent).
- Major organ failure.
- Diabetes.
- Chronic heart failure or other significant cardiac disease.
- Smoke (> 20 packs per year).

Version 3.0, 29 Nov 2016

PRODIGY CIP

- COPD or other significant pulmonary disease (including respiratory events before ward admittance).

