7.6 Derived variables

The statistical evaluations will use some derived variables as listed below. All additional derived variables or changes on the variable listed below are reported in the Statistical Programming Requirements document.

New Variables	Derivation
Monitoring Exposure (minutes)	End monitoring date/time – Start monitoring date/time
Study Exposure (days)	(Study Exit date – date of enrollment)/30.44
BMI35	If BMI >35 then BMI35=1 otherwise BMI35=0
Obese	If BMI >30 then Obese=1 otherwise Obese=0
AGE50	If Age >50 then AGE50=1 otherwise AGE50=0
AGE65	If Age >65 then AGE65=1 otherwise AGE65=0
STOP BANG SCORE	The score is the sum of the following points for each patient: If Snoring loudly= Yes then add 1 point If Tiredness in daytime= Yes then add 1 point If Observed apnea during sleep= Yes then add 1 point If Treated for High blood Pressure= Yes then add 1 point If Body mass index >35 (kg/m2) then add 1 point If Age >50 years then add 1 point If Neck circumference >40 cm (16 inches/17inches according to gender) then add If Gender = Male then add 1 point
Opioids Tolerant §	The FDA definition will be used: A patient is considered opioid tolerant if for at least 1 week he/she has been receiving one of the following: 
 • 60 mg oral morphine/day • 25 mcg transdermal fentanyl/hour • 30 mg oral oxycodone/day • 60 mg oral hydrocodone/day • 8 mg oral hydromorphone/day • 25 mg oral oxymorphone/day • Equi-analgesic dose of any other opioid The Morphine Milligrams Equivalent will be used.
STOP BANG SCORE Class	If 0≤STOP-BANG score ≤2 then STOP BANG SCORE Class= 1 labeled as “Low risk of OSA” If 3≤STOP-BANG score ≤4 then STOP BANG SCORE Class= 2 labeled as “Intermediate risk of OSA” If 5≤STOP-BANG score ≤8 then STOP BANG SCORE Class= 3 labeled as “High risk of OSA”
High Risk Surgery	If occurred within 24 hours
Known or suspected sleep-disordered breathing§	if “Yes to OSA (from Medical History) + YES to first 4 questions of the Apnea History
PCA or epidural or intrathecal therapy	PCA with route as epidural or intrathecal from CM
Multiple opioid or concurrent CNS/sedating medication	According to the Medication coding *(benzodiazepines, sleep aids, muscle relaxant, etc.)
Opioid dosage	According to the Medication coding * (>30mg oral morphine per day or equivalent)
Major organ failure	According to the coding °
Diabetes	if “Yes to Diabetes type I or II”

New Variables§	Derivation

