7.10.1.1 Deriving the model

Note for Programmer: The analysis for the primary objective will be performed on a Dataset with one row per patient with RD episode as validated by CEC as the dependent variable (at least one RD) and baseline predictors as independent variables. Potential predictors will be reported on continuous scale or grouped into categories.

The logistic model will be used for bivariate e multivariate odds ratios (ORs) and 95% confidence intervals (95% CIs) will be estimated for each potential predictor. The following steps will be followed to derive the score for each predictor according to categories⁴:

- Determine categories for each risk factors (the most will be 0/1)
- Determine reference class for each risk factor (for dummy the reference category is 0)
- Calculate mid-values to represent categories
- Determine multiplier β
- Determine point score for each risk factor category

If **Data Split** approach:

- Repeat multivariate model on the validation set
- Calculate performance measures
- The "Optimism" is the difference between the performance measures from validation and derivation set

If **Bootstrapping** approach:

- 500 bootstrapped replications of the multivariate model

- Calculate performance measures bootstrapped
- The difference between the bootstrapped performance and the model performance will be averaged to obtain an estimation of the “optimism” of the model. The optimism will be used to validate the model.

Table 25 - RD Risk Score Derivation identified by logistic – MFAS

Predictors	Bivariate analysis OR (95% CI) (N=XXXX)	Multivariate analysis OR (95% CI) (N=XXXX)	Coefficient	Adjusted Coefficient	Risk score point
Char#1	x.xx (x.xx- x.xx)	x.xx (x.xx- x.xx)	x.xxx	x.xx (x.xx- x.xx)	xx
Char#2	x.xx (x.xx- x.xx)	x.xx (x.xx- x.xx)	x.xxx	x.xx (x.xx- x.xx)	xx
...					
Char#N	x.xx (x.xx- x.xx)	x.xx (x.xx- x.xx)	x.xxx	x.xx (x.xx- x.xx)	xx

The collinearity between categorical variables will be also tested by means the Cramer V test for nominal variables and Kendal’s tau-b for ordinal variables. The multivariate logistic regression model will be performed using a stepwise selection procedure in which the presence of event will be the dependent variable. Independent predictors will be entered in to the model if a significant association, defined as $p \leq 0.05$, will be identified from bivariate analysis and, to avoid over-fitted and unstable model the correlation coefficient between them should be less than 0.25.

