The predictive risk score for RD, based on the best model selected from analysis above, will be calculated by multiplying each β coefficient taken from the final multivariate model by 10 and rounding to the nearest integer. The integers will then be added together to produce an overall RD risk score for each patient. The resulting continuous distribution of total risk scores across all patients in the derivation set will be then stratified into categories of points (depending on the total sample the quintiles or tertiles or optimal cutoff points) that grouped patients according to the level of risk.

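### SAP 7.6 narrows the PCA/epidural/intrathecal predictor to PCA by a neuraxial route, so intravenous PCA and non-PCA epidural opioids are coded unexposed

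*SAP*

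**What the plan says.** Protocol 13.1.1 names the predictor as "PCA or epidural or intrathecal therapy", three alternatives joined by 'or'. The row label in SAP 7.6 is identical, but the derivation beside it reads "PCA with route as epidural or intrathecal from CM".

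Other text bears on which meaning was intended:

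- Protocol 4.1 lists the ways opioids are given as separate items, including "by Patient Controlled Analgesia (PCA), by epidural or intrathecal infusions".
- Protocol 4.1 gives the known risk factors as including "comorbidities like preexisting pulmonary or cardiac disease, PCA use and smoking". SAP section 3 repeats this. Neither limits PCA by route.
- Protocol 8.4 excludes a subject when "Patient is receiving intrathecal opioids".

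The variable feeds the primary model. SAP 7.10.1.1 says "Independent predictors will be entered in to the model if a significant association" at p≤0.05 is found in the bivariate analysis. Score points are each final coefficient times 10, "rounding to the nearest integer. The integers will then be added together".

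SAP 7.6 also says that changes to the listed variables are reported in the Statistical Programming Requirements document.

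**The concern.** The label is a union and the rule is an intersection. If the rule is programmed as written, subjects whom the protocol counts as exposed go into the reference group and the coded-exposed group shrinks. Two outcomes are then possible, and they are alternatives:

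- **The predictor fails the entry screen.** A risk factor that the protocol chose in advance drops out of the score because of coding.
- **The predictor passes.** Its weight then comes from a small group, so it is unstable and, having been selected on significance, typically too large. A user reading the label would apply those points to intravenous PCA patients, whom the study counted as unexposed.

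Three other rows of the table also need attention, though no size is claimed for any of them. Smoking is labelled "Smoke (> 20 packs per year" but derived from any use. The cardiac and sleep-disordered-breathing rows join their conditions with a '+' that is not defined as AND or OR.

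**Working it through.** **1. The two definitions side by side**

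| Subject's opioid mode | Protocol 13.1.1 and SAP label | SAP 7.6 rule as written |
|---|---|---|
| Intravenous PCA | 1 | 0 |
| Epidural opioid, not PCA | 1 | 0 |
| Epidural PCA | 1 | 1 |
| Intrathecal opioid | 1, but excluded at entry | 1 only if PCA, but excluded at entry |
| None of these | 0 | 0 |

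This needs no assumption. No other SAP text gives a broader derivation, and SAP 7.12 announces no narrowing.

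**2. The plan's sample size, for context**

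10 events × 12 predictors = 120 events. 120/0.12 = 1000 derivation subjects. 1000 × 1.5 = 1500, and 1500 × 1.10 = 1650. The plan's figures reproduce, and recoding this predictor changes none of them.

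**3. Illustration of the effect**

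From the documents: 12% RD, n=1000 in the derivation cohort (or 1500 if the bootstrap option uses everyone), and the p≤0.05 entry rule. Assumed, because the documents give no values: intravenous PCA in 20–30% of subjects, epidural in 2–10% with half of it as PCA, no intrathecal, and one true OR for all routes.

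Let P be the true exposed share. Solve (1−P)·p0 + P·p1 = 0.12 with odds(p1) = OR × odds(p0). With e the epidural-PCA share, the coded-unexposed risk is (0.12 − e·p1)/(1 − e).

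Worked case (intravenous PCA 20%, epidural 10%, OR 2.0):

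- P = 0.30 gives p0 = 0.096 and p1 = 0.1755.
- Miscoded share: 25/30 = 83%.
- Coded exposed: 50 subjects, with 50 × 0.1755 = 8.8 expected RD events.
- Coded-unexposed risk: (0.12 − 0.05 × 0.1755)/0.95 = 0.117.
- Apparent OR: (0.1755/0.8245)/(0.117/0.883) = 1.6.

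The chance of passing the screen comes from exact enumeration of the two binomials with a two-sided Wald test on the log OR. A table with a zero cell counts as not passing.

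Results for n=1000, true OR 2.0:

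| IV PCA / epidural | Miscoded | Coded exposed (expected events) | Apparent OR | Pass, protocol coding | Pass, SAP rule | Median OR given pass, protocol coding → SAP rule |
|---|---|---|---|---|---|---|
| 20% / 2% | 95% | 10 (1.8) | 1.7 | 89% | 10% | 2.1 → 5.1 |
| 20% / 10% | 83% | 50 (8.8) | 1.6 | 93% | 25% | 2.0 → 2.4 |
| 30% / 2% | 97% | 10 (1.7) | 1.6 | 93% | 8% | 2.0 → 5.1 |
| 30% / 10% | 88% | 50 (8.3) | 1.5 | 94% | 19% | 2.0 → 2.4 |

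The last column is bivariate, is conditional on an estimated OR above 1, and ignores other predictors.

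Other settings, SAP rule against protocol coding:

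| Setting | OR 2.0 | OR 1.5 |
|---|---|---|
| n=1000, IV PCA 20–30% | 8–25% vs 89–94% | 5–12% vs 45–55% |
| n=1000, IV PCA 5% | 13–37% vs 58–81% | 7–16% vs 24–38% |
| n=1500, IV PCA 20–30% | 11–33% vs 97–99% | 6.5–15% vs 61–72% |

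The mix of modes matters most. With 20% exposed, OR 2.0 and n=1000, the screen is passed 33%, 56% or 74% of the time when epidural PCA makes up 25%, 50% or 75% of all exposure, against 87% under protocol coding. At 100% there is no loss.

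**4. Smoking unit**

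Read literally, 20 packs a year at an assumed 20 cigarettes per pack is 400/365 = 1.1 cigarettes a day. Pack-years would be a much higher bar. Neither reading is the same as any use.

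**The case against.** The strongest reply is that the SAP cell is shorthand and the working code sits elsewhere. Neighbouring cells are not executable rules either, since some only point to a coding dictionary. The literal rule also names a route that is excluded at entry, which makes it an odd thing to have intended. Section 7.6 sends changes to the Statistical Programming Requirements document. The PCA row has no § mark of its own, but the repeated column header does carry one and may be meant to cover every row. All of this stands as a limit on what can be said about the code. It does not reconcile the label with the rule in the SAP, which is the document that fixes the analysis in advance.

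A second reply is that the size is assumed. That is correct: the prevalences, the PCA share of epidurals and the OR are not in the documents, and the range reaches no loss at all. The inflated-weight outcome is also the less likely branch, because under the SAP rule the item fails the screen 75–92% of the time in the OR 2.0, n=1000 block. The median of 5.1 arises only when 10 subjects are coded exposed.

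A third reply is that SAP 7.6 allows additional derived variables, so another PCA variable could be added. None is listed.

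**Conclusion.** The concern holds. That the SAP rule contradicts its own label and the protocol is certain from the text. The effect on the score is conditional on the rule being programmed as written, and the documents cannot fix its size. Under the stated assumptions the predictor would usually be lost at the screen even when the true OR is 2.0. The loss shrinks as epidural PCA makes up more of the exposure. This should be fixed because it concerns a pre-chosen predictor in the primary model and is cheap to correct. The smoking row is a secondary mismatch of no claimed size. The '+' rows are unclear but not shown to be wrong, and the conclusion does not rest on them.

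**What to change.** In SAP 7.6, before outcomes are linked, code the predictor 1 if PCA by any route, or any epidural opioid, or any intrathecal opioid is recorded, and 0 otherwise. This keeps the protocol's three branches. If the Statistical Programming Requirements document already has this rule, carry it into the SAP.

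In the same edit:

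- **Smoking:** state the unit and make the rule match the label, or relabel both the predictor and the score item as any smoking.
- **Cardiac and sleep-disordered-breathing rows:** replace '+' with AND or OR.

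The cost is a SAP table edit and derived-dataset code, with sample size and endpoint unchanged. The SAP rule itself takes PCA and route from the medication data, so those inputs appear to exist. No eCRF was supplied, so whether smoking quantity was collected must be checked before choosing between the two smoking options.

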 9.1 Measures for model validity19

 9.2 Bootstrap Method21

 9.3 Detection Tool21

9.4 Priority List21

1 Version History

SAP Change History				
Version	Version Date	Description of Change	Paragraphs involved	Modified by
1.0	19 Jan 17	First Release	All	[name]
2.0	25 Jan 18	Change in Population set to be analyzed Add new sections 9.3 and 9.3	7.1.3 9	[name]

2 List of Abbreviations and Definitions of Terms

Abbreviation	Definition
ASA PS	American Society Anesthesiologists Physical Status
ASA	Apnea-Sat Alert™ Algorithm
CHF	Chronic Heart Failure
CIP	Clinical Investigation Plan
COPD	Chronic obstructive pulmonary disease
EAC	Episode Adjudication Committee
EC	Ethics Committee
ER	Emergency room
EtCO₂	End Tidal CO ₂
FAS	Full Analysis Set
GEE	Generalized Estimating Equation
ICH	International Conference on Harmonization
ICH E3	ICH guideline E3: Structure and content of clinical study reports
ICH E6	ICH guideline E6: Guideline for Good Clinical Practice
ICH E9	ICH guideline E9: Statistical principles for clinical trials
ICU	Intensive Care Unit
IPI	Integrated Pulmonary Index
OR	Operative Room
ORADE	Opioid Related Adverse Drug Event
PACU	Post Anesthetic Care Unit
PCA	Patient-Controlled Analgesia
PPV	Positive Predictive Value
PPS	Per Protocol Set
PRD	Potential Respiratory Depression event
RD	Respiratory Depression
RR	Respiratory Rate
SAP	Statistical Analysis Plan
SpO₂	Pulse Oximetry
STOP-BANG	S noring loudly, T iredness in daytime, O bserved apnea during sleep, high blood P ressure, B ody mass index >35 kg/

	m2, Age >50 years, Neck circumference >40 cm, and Gender
--	--

3 Introduction

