Chronic heart failure or other significant cardiac disease	if "Yes to CHF (from Medical History) + YES to any of the followings from Medical History: Coronary artery disease, Myocardial infarction, Stroke, Transient ischemic attack (TIA), Mitral valve disease, Aortic valve disease, Aortic aneurysm, Cerebral aneurysm, Peripheral vascular disease, Hypertension.
Smoke (> 20 packs per year)§	if "Yes to Smoke (any usage)"

* WHO Drug Dictionary, Version 2009MAR

° MedDRA dictionary, version 20.0

§ all details or potential changes in derived variable are listed in the Statistical Programming Requirements Document.

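### SAP 7.6 labels the smoking predictor as more than 20 packs per year, as the protocol does, but derives it as any smoking

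*SAP*

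**What the plan says.** **Smoking.** Protocol 13.1.1 names 12 literature-based variables for the prediction rule. One is "Smoke (> 20 packs per year". SAP 7.6 uses the same label for the derived variable and gives its derivation as "Yes to Smoke (any usage".

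**STOP-BANG neck item.** The scoring rule in SAP 7.6 reads "If Neck circumference >40 cm (16 inches/17inches according to gender) then add". It does not say which limit belongs to which gender. The STOP-BANG entry in SAP section 2 (abbreviations) has only "Neck circumference >40 cm, and Gender", with no inch values and no split by gender.

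**High Risk Surgery.** Protocol 13.1.1 lists high-risk surgery with a 24-hour limit. The whole derivation in SAP 7.6 is "If occurred within 24 hours".

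**Deferral.** SAP 7.6 opens by saying "All additional derived variables or changes on the variable listed below are reported in the Statistical Programming Requirements document". A footnote to rows marked §, including the smoking row, adds that "all details or potential changes in derived variable are listed in the Statistical Programming Requirements Document". That document is not among those available here.

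**Use in the score.** Under SAP 7.10.1.1, a predictor enters if its bivariate p-value is at most 0.05 and its correlation with the other predictors is below 0.25. Stepwise selection follows. Points are ten times the coefficient, rounded to an integer.

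**The concern.** For smoking, the label and the rule describe different exposures. A programmer who follows the rule codes every smoker as 1. A reader of Table 25, or a user of the finished score, sees the threshold in the label and gives the points only to smokers above it, although the coefficient was estimated on all smokers. Other rows of the same table carry their thresholds (BMI above 30, age above 65, opioid dose above 30 mg oral morphine equivalent), so the missing amount is not a convention of the table.

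If lighter smokers carry less excess risk than heavier ones, pooling them moves the estimated odds ratio towards 1. That lowers the points and makes it less likely that smoking passes the bivariate screen.

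The neck item has a similar fault on a smaller scale: one line states limits in two units that are not all the same limit, so the STOP-BANG score and class could differ between two programmers working from the same text.

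**Working it through.** **1. Smoking, texts side by side.**

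- Protocol 13.1.1: amount above 20 packs per year.
- SAP 7.6, label: amount above 20 packs per year.
- SAP 7.6, derivation: any usage.

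A smoker below the threshold is 0 under the first two and 1 under the third. The contradiction needs no calculation.

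**2. What dilution could do to the points.** The documents give no smoking prevalence and no smoking odds ratio, so this is an illustration. The assumptions are:

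- RD risk p0 = 12% in non-smokers and in smokers below the threshold. The 12% is the plan's assumed overall incidence, borrowed as a baseline.
- Smokers above the threshold have true odds ratio OR against non-smokers.
- A share s of all smokers, 25% to 75%, is above the threshold.

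Formulas:

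- baseline odds o = p0/(1 − p0) = 0.12/0.88 = 0.1364
- risk above the threshold pH = OR·o/(1 + OR·o)
- risk in any smoker p = s·pH + (1 − s)·p0
- estimated OR = [p/(1 − p)]/o
- points = 10·ln(OR), rounded

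Example with OR = 2.0 and s = 0.25: pH = 0.2727/1.2727 = 0.2143; p = 0.25 × 0.2143 + 0.75 × 0.12 = 0.1436; odds = 0.1436/0.8564 = 0.1676; estimated OR = 0.1676/0.1364 = 1.23. Points fall from 10·ln 2.0 = 6.9 (7) to 10·ln 1.23 = 2.1 (2).

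| True OR (points) | s = 25% | s = 50% | s = 75% |
|---|---|---|---|
| 1.5 (4) | 1.12 (1) | 1.24 (2) | 1.37 (3) |
| 2.0 (7) | 1.23 (2) | 1.47 (4) | 1.73 (5) |
| 3.0 (11) | 1.42 (4) | 1.89 (6) | 2.42 (9) |

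**3. Sample size.** The plan's figure follows from 12 × 10/0.12 = 1000; 1000/(2/3) = 1500; 1500 × 1.10 = 1650. Recoding or relabelling smoking leaves 12 candidates, so 1650 does not change.

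**4. Neck limit.** At 2.54 cm per inch:

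- 40 cm = 40/2.54 = 15.75 in.
- 16 in = 40.64 cm, 1.6% above 40 cm, which is consistent with rounding.
- 17 in = 43.18 cm, which is 3.18 cm or 8.0% above 40 cm (3.18/40) and is not rounding.

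A subject of the gender given the 17-inch limit, with a neck above 40 cm and up to 43.18 cm, scores 1 on the centimetre rule and 0 on the inch rule. One point changes the STOP-BANG class for totals at the 2/3 or 4/5 boundary.

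**5. Is STOP-BANG in the primary score?** It is not among the 12 variables in Protocol 13.1.1. The sleep-disordered-breathing predictor in SAP 7.6 is built from OSA history and the first four apnea-history questions, not from the STOP-BANG total or class.

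**6. High Risk Surgery.** The protocol's only quantity, 24 hours, is kept in the SAP. Neither document defines high risk or says from what time the 24 hours are counted.

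**The case against.** **Deliberate change with a stale label.** SAP 7.10.1.1 leaves the categories of each risk factor to be set, SAP 7.12 allows departures from the protocol because of data availability, and Protocol 13.2 lets changes that do not alter a principal feature be justified in the final report. Any-usage coding may be intended, and the programming document may say so. This stands as a possible explanation, and it is why relabelling is an acceptable repair. It does not cure the SAP: the rule and label still disagree there, and SAP 7.12 does not mention smoking.

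**The consequence is conditional.** Smoking must pass the bivariate screen, the correlation limit and stepwise selection before it earns points, and the wrong label must survive into the tool. Dilution also requires lower excess risk below the threshold. Both points stand. Moreover, read literally the threshold is a rate of 20/52, or about 0.4 packs a week. If so, the share of smokers above it could exceed 75%, and the loss of points would be smaller than in the table.

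**Stronger readings the documents do not support.** A reader might infer that High Risk Surgery is coded as any surgery within 24 hours, making two of the 12 predictors mislabelled. The SAP does not say this: the row is named for high-risk surgery, and the natural subject of its rule is that surgery. Because the protocol also leaves high risk undefined, the two documents do not conflict. A reader might also infer that STOP-BANG scores will vary by region through the unit each site uses. The documents do not state the recording unit, and Protocol section 6 provides for common procedures and one database.

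**Conclusion.** The smoking contradiction is certain on the text and affects one of the 12 candidate predictors. As written, SAP 7.6 either mis-codes the variable against the protocol or mislabels it.

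The numerical effect is illustrative. With no excess risk below the threshold, 12% baseline risk and 25% to 75% of smokers above the threshold, a true odds ratio of 2.0 is estimated as 1.23 to 1.73, so 7 points become 2 to 5. If lighter smokers carry the same risk as heavier ones there is no dilution, and only the wrong label remains.

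The neck inconsistency is real for the 17-inch limit alone. It bears on the STOP-BANG score and class, with no shown effect on the primary score. High Risk Surgery is a missing definition, not an error in coding. It would go too far to conclude that the final score will be wrong: that depends on variable selection and on a programming document that cannot be seen here.

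**What to change.** 1. **Smoking.** In SAP 7.6, code the variable from the recorded amount at the threshold in Protocol 13.1.1, with the unit spelled out. If the amount was not collected, relabel the predictor as any smoking in SAP 7.6, Table 25 and the score, and record this as a change from Protocol 13.1.1 with the reason.
2. **Neck item (secondary).** State one rule in one unit, either a single limit or a limit for each gender, say which limit applies to which gender, and make the entry in SAP section 2 agree.
3. **High Risk Surgery (wording).** State what counts as high risk and the time from which the 24 hours run.

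The cost is a few lines of SAP text and matching program code. Relabelling needs no new data. Coding by amount makes the smoking category smaller, so its coefficient may be less precise. The planned 1650 subjects are unaffected.
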